7.3 Rescue Medications

All rescue medications (ie, any medication used to treat symptoms of an acute allergic reaction) must be recorded on the case report form. The adverse event requiring the use of rescue medications must be recorded on the adverse event case report form and in the subject's source documents.

Medications for the treatment of individual acute allergic reactions (eg, antihistamine, epinephrine, IV fluids, beta-adrenergic agonist [eg, albuterol by inhaler or nebulizer], oxygen, glucocorticosteroids) are to be used as indicated.

An epinephrine auto-injector device will be provided or prescribed as appropriate to parents/caregivers who do not have one. The expiration date and record of training on the epinephrine auto-injector device must be documented in the subject's source documents.

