8.3 Adverse Event Definitions

This section provides definitions for adverse events, adverse reactions, serious adverse events, unexpected adverse events, SUSARs, and adverse events of interest for all subjects.

Adverse event: Any unfavorable and unintended sign (including an abnormal laboratory finding considered clinically significant by the investigator), symptom, or disease temporally associated with the study treatment, whether or not related to the study treatment.

Examples of adverse events include the following:

- A new event or experience that was not present at screening/baseline
- A worsening, excluding minor fluctuations, in the nature, severity, frequency, or duration of a pre-existing condition
- An investigational abnormality (eg, laboratory tests, vital signs) **only if the abnormality is considered clinically significant** by the investigator (eg, associated with clinically significant symptoms, requires additional diagnostic testing or intervention, leads to change in study product dosing or discontinuation from the study). If a clinically significant abnormality is considered a symptom of a diagnosed condition, then the condition is to be documented as the adverse event

An adverse event **does not** include the following:

- Pre-existing diseases or conditions present or detected before the start of study treatment that do not worsen
- SPT reactions, unless the reaction or a complication from the procedure is considered a serious adverse event
- Situations where an untoward medical event has not occurred (eg, planned hospitalization for an elective procedure)

Adverse reaction: Any adverse event considered related to study product dosing.

Serious adverse events: Any adverse event that meets any of the criteria in [Table 6](#) as determined by the investigator or sponsor.

Table 6: Criteria for Serious Adverse Events

Subject Outcome	Comments
Death	Death is an outcome, not an adverse event. The primary adverse event resulting in death should be identified.
Life-threatening	At immediate risk of death from the adverse event (eg, from the combination of severe anaphylaxis and a grade 4 allergic reaction per Section 8.5).
Inpatient hospitalization or prolongation of existing hospitalization	Does not include prolonged hospitalization for extended observation (eg, to watch for a delayed or biphasic reaction) or planned hospitalization (eg, for an elective procedure).

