8.6.6 Adverse Events of Interest

Adverse events of interest include anaphylaxis, GI adverse events with prolonged dose interruption (> 7 consecutive days) or that result in early discontinuation, accidental and nonaccidental food allergen exposure, severe adverse events, and use of epinephrine. These events require rapid reporting as described in [Section 8.7.2](#).

Allergic reactions during DBPCFCs will not be considered related to study product or reported as adverse events of interest.

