8.7.2.1 Serious Adverse Events Reporting

Study site personnel will report serious adverse events to the sponsor or designee using the appropriate case report form in accordance with the information requested on the form. Serious adverse events reported to the investigator after the safety reporting period are to be reported to the sponsor if the investigator assesses the event as related to the study product.

If a subject dies, the reported information should include the cause of death as the event term (with fatal outcome), whether the event leading to death was related to study product, the autopsy findings if available, and any other supporting data (eg, death certificate, hospital/study site notes).

Allergic reactions during DBPCFCs that meet the criteria for serious will be reported as related to the procedure.

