10.6 Analysis of Safety

All safety analyses will be performed using the safety population. Safety data will be summarized and listed by treatment received.

Safety data will be collected from signed informed consent and assent (where required) through 14 days after the last dose of study product, or through study exit for subjects receiving AR101 treatment in a follow-on study. Safety follow-up data will be collected for at least 30 days after early discontinuation or study exit for subjects with unresolved adverse events, or for at least 6 months after early discontinuation or study exit for subjects with GI adverse events of interest.

Adverse events will be classified by system organ class and coded to preferred term using MedDRA. Adverse events will be classified by severity using the CoFAR grading system for allergic reactions, modified EAACI guidelines for anaphylaxis, and CTCAE for all other adverse events ([Section 8.5](#)).

Summaries of the safety of AR101 and placebo treatment during the study will include the following:

- Overall summary of adverse events
- Incidence of all nonserious and serious adverse events
- Incidence of adverse events by severity grade
- Incidence of adverse events during up-dosing and maintenance
- Incidence and severity of treatment-related adverse events
- Incidence of treatment-related adverse events during up-dosing and maintenance
- Incidence of dose modifications
- Exposure-adjusted event rates for the most frequent adverse events (ie, adverse events in $\geq 5\%$ of the safety population)
- Exposure-adjusted event rates for the most frequent treatment-related adverse events (ie, adverse events in $\geq 5\%$ of the safety population)

- Incidence of early treatment discontinuation due to adverse events and due to chronic or recurrent GI adverse events
- Separate summaries will be presented for anaphylaxis, allergic reaction adverse events, use of epinephrine, and accidental/nonaccidental food allergen exposure

Adverse events with onset before the first dose of study treatment will be listed only.

All medications will be coded using the World Health Organization Drug Dictionary (WHO-DD). Medications will be listed and summarized by Anatomical Therapeutic Chemical (ATC) classification system level 1 and preferred name.

- Prior and concomitant medications, excluding rescue medications, will be summarized separately by ATC class, preferred name, and treatment.

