- Rescue medications used during screening, initial dose escalation, up-dosing, maintenance, and overall (including all rescue medications reported on the case report form) will be summarized by ATC class, preferred name, and treatment received.
- All prior, concomitant, and rescue medications will be listed by subject.

Summary statistics will be provided for the TRACK, EASI, and laboratory data if relevant. These data will also be listed by subject.

Full details for the safety analyses will be provided in the statistical analysis plan.

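### Section 10.6 does not separate exit food-challenge reactions and treatments from on-treatment safety data, so the unrestricted summaries can understate an AR101 excess

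*Combined protocol and SAP*

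**What the plan says.** **Definition and window.** Section 8.3 lists what is not an adverse event. The list includes "SPT reactions, unless the reaction or a complication from the procedure is considered a serious adverse event" but does not name food-challenge reactions. Under Section 8.7.1, collection runs to 14 days after the last dose, or to study exit for children entering the follow-on study. Section 5.4 makes both exit-challenge days part of completing the study.

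**Recording.** Section 7.3 states: "The adverse event requiring the use of rescue medications must be recorded on the adverse event case report form". Appendix 1 sends challenge signs and symptoms to source documents, and challenge treatments to case report forms as well.

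**Attribution.** Section 8.6.6 says: "Allergic reactions during DBPCFCs will not be considered related to study product or reported as adverse events of interest". Section 8.7.2.1 adds: "Allergic reactions during DBPCFCs that meet the criteria for serious will be reported as related to the procedure".

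**Analysis.** Section 10.6 has one exclusion by onset: "Adverse events with onset before the first dose of study treatment will be listed only". It plans overall, severity-grade and exposure-adjusted summaries, and then: "Separate summaries will be presented for anaphylaxis, allergic reaction adverse events, use of epinephrine, and accidental/nonaccidental food allergen exposure". Rescue medication is summarized for screening, initial dose escalation, up-dosing, maintenance and "overall (including all rescue medications reported on the case report form". There is no row for the exit challenge. Full details are deferred to the SAP.

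**The concern.** The exit challenge deliberately provokes reactions with up to 4043 mg of cumulative peanut protein, and successful treatment makes those reactions less frequent on AR101. The onset rule in Section 10.6 removes the screening challenge from the adverse event tables and leaves the exit challenge in. An all-causality table that pools provoked reactions with reactions to daily dosing therefore carries part of the efficacy effect into the safety comparison.

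Safety and tolerability is a secondary objective, and allergic reactions are the main expected harm. The exit-challenge reactions are already used for efficacy, through the tolerated-dose endpoints and maximum symptom severity. Counted again as adverse events, they would make AR101 look better tolerated than its daily dosing is.

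**Working it through.** **1. Which tables are touched.** Setting the rules in Sections 7.3, 8.3, 8.6.6, 8.7.1 and 10.6 side by side:

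| Summary | Exit-challenge reactions or treatments |
|---|---|
| Overall, severity grade, allergic reaction, all-causality exposure-adjusted | Enter if on the adverse event form; no exclusion stated |
| Overall rescue-medication row | Treatments enter; the row takes everything on the form |
| Anaphylaxis, epinephrine | Unclear: both belong to the class that Section 8.6.6 closes to challenge reactions, but Section 10.6 does not say its summaries follow that class |
| Treatment-related | Out, by Section 8.6.6 |
| Up-dosing and maintenance | Out; the challenge follows maintenance (Section 3.1) |

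**2. The plan's own figures.** The documents give no figure for this point. The response rates needed come from Section 10.3, and the power stated there reproduces with the Farrington-Manning method, 88 versus 44 children, two-sided 0.05:
- 55% versus 15%, margin 0.15: 85.0% (stated 85%).
- 50% versus 10%, margin 0: 99.9% (stated > 95%).

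**3. Share reacting at the exit challenge.** Reactors = completers − responders. This takes 75% completing in each arm and treats every completer who does not tolerate the dose as a reactor.
- By 600 mg: AR101 75 − 55 = 20%; placebo 75 − 15 = 60%.
- By 1000 mg: AR101 75 − 50 = 25% (22 of 88); placebo 75 − 10 = 65% (28.6 of 44).
- If half of those tolerating 1000 mg react at 2000 mg: AR101 25 + 25 = 50% (44 of 88); placebo 65 + 5 = 70% (30.8 of 44).

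**4. Effect on an epinephrine contrast.** Let b be on-treatment use: 14.0% AR101 and 6.5% placebo, from ARC003 (Section 1.2.2). Let r be the reactor share and q the assumed share of reactors given epinephrine. Treating the two sources as independent:

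combined use = 1 − (1 − b)(1 − r·q)

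| q | AR101, r = 25% | Placebo, r = 65% | Difference (points) |
|---|---|---|---|
| 0% | 14.0% | 6.5% | +7.5 |
| 10% | 16.1% | 12.6% | +3.6 |
| 20% | 18.3% | 18.7% | −0.4 |
| 50% | 24.8% | 36.9% | −12.1 |

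With reactions at 2000 mg included (r = 50% and 70%):
- q = 20%: 1 − 0.86 × 0.90 = 22.6% versus 1 − 0.935 × 0.86 = 19.6%, or +3.0 points.
- q = 50%: 1 − 0.86 × 0.75 = 35.5% versus 1 − 0.935 × 0.65 = 39.2%, or −3.7 points.

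**5. Reversal point.** Setting the arms equal, with A for AR101 and P for placebo:

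q* = (b_A − b_P) / [(1 − b_P)·r_P − (1 − b_A)·r_A]

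- By 1000 mg: 0.075 / (0.935 × 0.65 − 0.86 × 0.25) = 0.075 / 0.39275 = 19.1%.
- With the 2000 mg scenario: 0.075 / (0.6545 − 0.430) = 33.4%.
- If only 20% of AR101 and 5% of placebo children tolerate 2000 mg (r = 55% and 70%): 0.075 / (0.6545 − 0.473) = 41%.
- With ARC003's own completers not tolerating 1000 mg (AR101 296 × 0.368 / 372 = 29.3%; placebo 116 × 0.974 / 124 = 91.1%): about 12.5%.

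The denominator is positive in each case, so pooling shrinks the AR101 excess at any q above zero. Reversal depends on q.

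**The case against.** The case against has several parts, and much of it stands.

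- **Adverse events of interest.** Section 8.6.6 says "Adverse events of interest include anaphylaxis, GI adverse events with prolonged dose interruption (> 7 consecutive days) or that result in early discontinuation", and also lists food allergen exposure and epinephrine use. Challenge reactions are not reported in that class, so reading the anaphylaxis and epinephrine summaries as summaries of that class is natural. Entry into those two is therefore not established. Allergic-reaction adverse events as such are not in the class, so this does not clear that summary or the overall, severity and exposure-adjusted ones.
- **Recording.** Appendix 1 routes challenge symptoms to source documents, whereas Section 8.6.1 puts symptoms of study-product reactions on the case report form too. Untreated challenge reactions may never reach the adverse event form. Treated ones do under Section 7.3, and the two routes are not reconciled.
- **Other tables.** The treatment-related and by-period tables would still show an AR101 excess, and maximum severity at the exit challenge is already tabulated by arm. This limits the harm but does not repair the unrestricted summaries.
- **Evidence on q.** In ARC002 (Section 1.2.1), 60% of 40 children and adults tolerated 1000 mg, so 16 did not, and two needed epinephrine: 2/16 = 12.5%. With r = 25% and 65% that gives 16.7% versus 14.1%, diluted but not reversed. Those subjects were older and all AR101-treated, so this is indicative only.
- **The ARC003 baseline.** Those rates are for ages 4 to 17, and the text does not say whether challenge use is included. If it is, adding it again double counts.
- **Deferral.** Safety details are left to the SAP. If a rule there already separates the challenge, only a cross-reference is needed; nothing in the reviewed text shows one.

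**Conclusion.** The point holds for the unrestricted summaries. Applied literally, Section 10.6 mixes provoked and on-treatment reactions in the overall, severity-grade, allergic-reaction and all-causality exposure-adjusted tables, to the extent that they reach the adverse event form. It mixes challenge treatments into the overall rescue-medication row. For anaphylaxis and epinephrine, the text leaves the question open.

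On the plan's rates the mixing is unequal, about 25% versus 65% of each arm by 1000 mg, and it dilutes an AR101 excess. Reversal in the epinephrine illustration needs q above about 19%, or about 33% in the 2000 mg scenario. That rests on an assumed q, ARC003 rates taken as treatment-period use, independence and equal dropout.

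A reader might infer that the safety analysis as a whole hides or reverses the harm of AR101, or that most children who react are on placebo. The documents support neither. The treatment-related and by-period tables are untouched. Placebo is higher as a proportion, but with 2:1 allocation the counts are 22 versus 28.6 by 1000 mg and 44 versus 30.8 in the 2000 mg scenario.

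This should be corrected because it affects a secondary objective. It does not touch the primary analysis.

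**What to change.** Add a rule to Section 10.6, in line with Section 8.6.6 and cross-referenced from Section 8.3:

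- Flag reactions and rescue medication with onset during the exit challenge or its observation period.
- Leave flagged records out of the on-treatment adverse event, severity, anaphylaxis, allergic-reaction, epinephrine, exposure-adjusted and overall rescue-medication summaries.
- Tabulate them separately by arm and challenge dose.
- Keep serious challenge reactions reported as procedure-related, as Section 8.7.2.1 already requires.
- State whether untreated challenge symptoms go on the adverse event form, so that Appendix 1 and Section 7.3 agree.

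The cost is a few sentences, a flag on the adverse event and medication records, and one extra table. No new data are needed. Because Section 3.3 unblinds children one by one after exit, the rule is best settled before assignments become known.

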10.7 Analysis of Exploratory Endpoints

Exploratory endpoints will be assessed as follows:

- Change from baseline in peanut-specific and peanut component-specific serum immunoglobulins.
- Change from baseline in mean wheal diameter and mean erythema diameter on SPT to peanut.
- Change from baseline in TRACK and EASI scores.
- Palatability of study treatment, assessed using a palatability survey.
- Proportion of subjects who tolerate a single highest dose of 2000 mg peanut protein (4043 mg cumulative) during the exit DBPCFC.
- Change from baseline in the single highest tolerated dose of peanut protein at the exit DBPCFC.
- Maximum dose of peanut protein reached with no more than mild allergy symptoms at the exit DBPCFC

Full details for these analyses will be provided in the statistical analysis plan.

11 STUDY COMMITTEES AND COMMUNICATIONS

An independent, external DSMC will be established to monitor the study for safety. The committee will meet on a periodic basis to review the study safety data in accordance with the DSMC charter.

12 LABORATORY REQUIREMENTS

12.1 Clinical Laboratory Tests

Clinical laboratory tests (hematology, immunology) will be performed according to the schedules of activities ([Appendix 4](#), [Appendix 5](#)). Samples will be stored until the specified analyses are completed and then will be destroyed in accordance with standard laboratory practice and applicable local regulations.

A list of the required clinical laboratory tests and other evaluations is provided in [Table 18](#). All samples for laboratory analysis must be collected, prepared, labeled, and shipped according to laboratory requirements. All clinical laboratory tests required for this study will be performed by the central laboratory specified in Form FDA 1572 Section 4 unless otherwise specified. The central laboratory reference ranges will be used.

A local clinical laboratory may be used to assess samples at unscheduled visits or urgent care to evaluate an adverse event. Central laboratory samples should also be obtained whenever possible during unscheduled visits. Example pediatric reference ranges for clinical laboratory tests are provided in [Appendix 2](#). No local laboratory data will be entered into the study database and local laboratories will not be included on Form FDA 1572.

Clinical laboratory test results that are assessed as abnormal and clinically significant are to be documented on the adverse event case report form ([Section 8.7](#)). If a clinically significant abnormality is considered a symptom of a diagnosed condition, then the condition is to be documented as the adverse event.

Additional details are provided in the laboratory manual.

Table 18: Clinical Laboratory Tests

Hematology	Immunology
Red blood cell count	Total immunoglobulin (Ig) E
Hemoglobin	
Hematocrit	Peanut-specific IgE and components (Ara h 1, Ara h 2, Ara h 3, Ara h 8, Ara h 9)
Platelet count	
White blood cell count with differential (percent and absolute)	Peanut-specific IgG4 and components (Ara h 1, Ara h 2, Ara h 3, Ara h 8, Ara h 9)
• Total neutrophils	
• Lymphocytes	
• Monocytes	
• Eosinophils	
• Basophils	

The total volume of blood collected is not to exceed 2 mL/kg per day (maximum 4 mL/kg in a 30-day period) or per local requirements.

12.2 Optional Immune Study to Assess Cellular Responses to Peanut Antigen

Optional blood samples for evaluation of cellular responses to peanut antigen using the basophil activation test (BAT) and mast cell activation test (MAT) will be collected at certain study sites according to the schedules of activities ([Appendix 4](#), [Appendix 5](#)). The BAT and MAT will be performed at specified study site laboratories and use flow cytometry to measure CD63 upregulation, a marker of basophil and mast cell activation in IgE-mediated responses to peanut antigen ([Santos, 2018](#); [Santos, 2014](#)). The BAT will be conducted in whole blood collected in heparin-containing tubes and tested within 24 hours of collection. Plasma samples will be used to sensitize a mast cell line and mast cell activation in response to peanut antigen will be measured in a flow cytometric assay.

13 INVESTIGATOR AND ADMINISTRATIVE REQUIREMENTS

The sponsor must confirm that a study site is activated before an investigator enrolls subjects in the study, and the following documents must be available:

- Fully executed and signed Form FDA 1572
- Fully executed clinical trial agreement
- Current curriculum vitae from the investigator (also applies to all subinvestigators listed on the Form FDA 1572)
- Financial disclosure by the investigator (also applies to all subinvestigators listed on the Form FDA 1572)
- Investigator-signed protocol signature page
- Investigator-signed acknowledgment of receipt of the current investigator brochure
- EC and regulatory authority approval letter

- EC-approved informed consent and assent forms
- Additional documents as necessary per local requirements

If an investigator changes during the course of the study, the sponsor and any local regulatory authorities, as applicable, must first approve the change of investigator and the new investigator must provide the sponsor all of the relevant documents listed above.

The sponsor personnel or representatives may visit the study site, if necessary, before initiation of the study to review information with study site personnel about protocol requirements pertaining to the study treatment, case report forms, monitoring, serious adverse event reporting, and other relevant information.

13.1 Ethics

13.1.1 Ethics Committee

Before initiating the study, the investigator or sponsor will obtain confirmation from the EC that the EC is properly constituted and compliant with all requirements and local regulations.

The investigator or sponsor will provide the EC with all appropriate material, such as the protocol, current investigator brochure, site-specific informed consent form, assent form (where required), and other written information provided to the subjects. The study will not be initiated until the appropriate EC and regulatory authority approval is obtained in writing for all required documentation, and copies are received by the sponsor.

EC and regulatory authority approval will be obtained for any substantial protocol amendments and informed consent/assent revisions before implementing the changes. The investigator or sponsor will provide appropriate reports on the progress of the study to the EC, per local requirements, and to the sponsor or designee in accordance with applicable local regulations.

